A Device to Prevent Female Urinary Stress Incontinence

Principal Investigator: [name], Department of Urology.

Sponsor: Watkins-Conti Products, Inc.

Background and Significance of Study

Stress Urinary Incontinence (SUI) and Pelvic Organ Prolapse (POP) are growing problems globally that not only cost health care systems large amounts of money, but severely degrade the quality of life (QoL) of an estimated 40 million women in the United States alone. Although surgical solutions can succeed in ameliorating symptoms associated with SUI and POP, surgery is not without risks and complications and may even leave the patient in a worse situation than before treatment (1, 2). The FDA issued a Public Health Notification regarding surgical mesh placed through the vagina (transvaginal placement) to treat POP and SUI. The FDA identified serious and frequent complications including mesh erosion through the vagina, pain, infection, bleeding, discomfort during intercourse, organ perforation, urinary problems, recurrent prolapse, neuro-muscular problems, vaginal scarring/shrinkage & emotional problems. Most surgical complications require intervention including medical, additional surgical treatment and hospitalization. The pessary, which is most commonly used for management of female POP but also has been used for SUI, does present a viable non-surgical option for treating SUI and POP. Pessaries have few complications and side effects, however these devices are traditionally placed in the vagina for weeks at a time. Ideally the design should allow for easy removal and insertion by the patient (3). Difficulty with self-removal and insertion of the pessary and loss during defecation (Colpexin) may be limiting widespread use of the devices. Currently use of pessaries equates to a life-long commitment of office visits every 2 to 3 months.

Watkins-Conti Products, Inc., has developed a simple design that solves many of these problems and could provide a simple, inexpensive solution for SUI for many women. The Collapsible Cone-Shaped Intra-Vaginal Urinary Incontinence Support Device (Yoni.Fit) from 100% medical grade silicone, places pressure on the urethral sphincter while supporting pelvic organs, thus eliminating or significantly reducing urine leakage. Inspired by the ring pessary, the simple yet effective design of the collapsible device Yoni.Fit is user friendly, light weight and less difficult to hold in the vagina than the Colpexin. Yoni.fit is believed to assist with strengthening the pelvic floor like the Colpexin while supporting anatomy like the pessary, reducing the need for invasive surgeries altogether.

[figure not shown]
In order to support applications for Small Business Innovation Research funding and for investor funding, Watkins-Conti Products proposes to demonstrate short term efficacy with patients suffering from SUI for reduced or eliminated leakage against a standardized battery of challenges as a primary endpoint. Ease of use and support of anatomy with use of Yoni.Fit will serve as secondary endpoint

Specific Aims-
Aim: Test the acute efficacy of Yoni-Fit in a clinical trial of unselected women with incontinence in a standardized set of challenges performed with and without Yoni-Fit in place.

Protocol

The flow chart for the study is shown in the figure below.

Flow Chart for Feasibility Study

1. Subjects will be recruited in two ways. First, subjects will be referred from the patient bases of two physicians at the OUHSC who treat incontinence. These are [name] of the Department of Obstetrics and Gynecology and [name] of the Department of Urology. The second source will be a campus-wide email announcing the study. Regardless of the method, potential subjects will be referred to [name], a research coordinator for the study who is employed by the Department of Urology.
2. Potential subjects will be pre-qualified by a 6-item questionnaire, the Questionnaire for Urinary Incontinence Diagnosis (QUID) (4). This questionnaire has 3 questions each referring to the seriousness of Stress Urinary Incontinence (SUI) and of Urge Urinary Incontinence (UUI). Subjects will be accepted if their SUI score is 5 or greater and is greater than the UUI score. For privacy reasons, these scores will not be retained. Subjects will then be given an appointment. Subjects will be instructed to wear comfortable athletic type wear and not to drink any fluid for two hours prior to their appointment.
3. When they appear for their appointment, subjects will be administered the informed consent. All paperwork will be pre-numbered with a code that will link to the subject name. They key will be kept confidential by the Study Coordinator. They will be instructed to empty their bladders and will be given a liter of water or other drink and instructed to drink it over a 15-20 minute time period. An abbreviated patient history will be obtained for the purpose of establishing whether the subject meets the inclusion criteria and is not disqualified by meeting the exclusion criteria. The subject will again fill out the QUID questionnaire. The inclusion criteria are a SUI score of 5 or greater, predominately SUI (SUI score>UUI score) and age between 25 and 65. Exclusion criteria are predominantly UUI, prolapse greater than mild, hysterectomy or other pelvic floor surgery other than a Caesarian section, diabetes, BMI>35 or unable to perform ten

“jumping jack” exercises. Patients will be administered three additional questionnaires in order to compute a Severity Score. These questionnaires are the Urinary Distress Inventory (UDI), Urinary Impact Questionnaire (UIQ) and the Incontinence Severity Index (ISI). The scores will be multiplied together to provide the Severity Score.

4. Patients will then participate in an abbreviated Pad Test. This test has been validated (5). An hour after finishing the liter of liquid, the subject is given a tared incontinence pad, which is then put in place. She then engages in the following mild exercise challenges..
 - a. Stand from sitting 10 times.
 - b. Cough vigorously while standing.
 - c. Bend down to pick up small object.
 - d. Perform ten jumping jacks.

The subject then will remove pad, place into bag and seal. The Experimenter will then weigh pad. The subjects will be randomized so that half will perform the Abbreviated Pad Test with the Yoni.Fit device in place followed by repeating without the device in place. The other half will perform the challenges in the reverse order.

5. The experimenter will calculate a change in score, which is the weight of the pad worn without the device in place minus the tare weight of the pad divided by the weight of the pad with the device in place minus the tare weight of the pad. In case no urine is released with the device in place, the Improvement Score will be defined as “1000”. A Release Change will also be calculated as the net weight without the device in place minus the weight with the device in place divided by the net weight released without the device in place.
6. Patients will be paid \$100 for their participation.

Data Analysis

After checking the data for correctness, the data analysis will ensue. Descriptive statistics will be calculated and include the mean, median, standard deviation. The improvement scores will be correlated with the symptom scores and demographics to provide a preliminary estimate of how well the YoniFit performs and possibly to identify parameters that predict less than optimal prevention of SUI.

Budget

Item	Amount
Personnel	
[name], PI	\$9,251
[name], Clinical Coordinator	\$3,989
Per subject costs	\$38,250
IRB application and account set-up	\$3,000
Supplies and Miscellaneous Costs	\$1,000
Total direct cost	\$55,490
Clinical trial IDC (30%)	\$16,647
Grand Total cost	\$72,137

Budget Justification

[name] will act as overall PI for this project and will coordinate between Watkins-Conti Products and the OUHSC. He will meet with the clinicians as necessary and weekly with [name] to assess progress and solve any problems. He will also be responsible for preparing the IRB application and for the data analysis and for preparing a report. His cost is calculated on the basis of 1 person-month (8.33% effort) on a University salary of \$80,457 plus 37.98% fringe benefits.

[name] will act as the clinical coordinator. In addition to the per subject costs, she will also assist with preparing the IRB application, talk to patients who do not qualify, coordinate with the physicians and meet with [name]. Her cost is calculated on the basis of a salary of \$28,907 with 10% effort plus 37.98% fringe

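### The SUI > UUI entry rule tends to raise the correlation between the two QUID scores, so correlating response with each score alone can mislead about which one accompanies poor response

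*Combined protocol and SAP*

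**What the plan says.** Step 2 of the Protocol describes the QUID: "This questionnaire has 3 questions each referring to the seriousness of Stress Urinary Incontinence (SUI) and of Urge Urinary Incontinence (UUI". The same condition is applied twice. At pre-qualification, "Subjects will be accepted if their SUI score is 5 or greater and is greater than the UUI score", and of those results the plan says "For privacy reasons, these scores will not be retained". At the visit, "The subject will again fill out the QUID questionnaire", and step 3 states the criteria: "The inclusion criteria are a SUI score of 5 or greater, predominately SUI (SUI score>UUI score". The visit QUID is therefore the only QUID available for analysis, and it comes from women who have already passed the rule.

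Step 3 also collects the UDI, UIQ and ISI: "The scores will be multiplied together to provide the Severity Score".

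The only predictor analysis is in Data Analysis: "The improvement scores will be correlated with the symptom scores and demographics". Part of its stated purpose is "possibly to identify parameters that predict less than optimal prevention of SUI". The plan does not list which scores count as symptom scores, and it mentions no regression, partial correlation or other analysis of two scores together.

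**The concern.** The entry rule cuts the plane of possible (SUI, UUI) pairs along a diagonal. Every woman above the line, with urge at or above stress, is removed. In what remains, the room for a high UUI score grows with the SUI score, which pushes their correlation upward even if the two scores have nothing to do with each other in the source population.

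If response is then correlated with one score at a time, two things can go wrong. A score with no effect of its own can look predictive because it travels with the other. And if stress severity goes with better response while urge symptoms go with worse, the two associations partly cancel, so both may be missed.

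The question is worth getting right because the device is described as pressing on the urethral sphincter and urge-predominant women are excluded. Whether residual urge symptoms accompany poor response is a natural thing to ask of these data.

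**Working it through.** The plan states no SUI-UUI correlation, sample size, alpha or power, so it has no figure to reproduce.

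**Inputs**
- Entry rule: SUI ≥ 5 and SUI > UUI (Protocol, steps 2 and 3).
- Sample size: not stated. The per-subject budget of $38,250 (Budget) divided by $765 per patient (Budget Justification) is 50. This is an inference.
- Assumed: subscale range (0–15 as the main case), source distributions, standardised effects of 0.4, two-sided 5% tests, and a roughly normal response.

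**Step 1: what the rule does to unrelated scores.** Take SUI and UUI as independent and uniform on 0–15. The admitted pairs have S = 5,…,15 and U = 0,…,S−1, which is ΣS = 110 pairs.
- E[S] = ΣS²/110 = 1210/110 = 11. E[S²] = ΣS³/110 = 14300/110 = 130. Var(S) = 130 − 121 = 9.
- E[U] = ½(1210 − 110)/110 = 5. E[U²] = Σ(2S³ − 3S² + S)/(6 × 110) = 25080/660 = 38. Var(U) = 38 − 25 = 13.
- E[SU] = ½(14300 − 1210)/110 = 59.5. Cov = 59.5 − 55 = 4.5.
- r = 4.5/√(9 × 13) = 0.416.

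The same enumeration gives 0.31, 0.38 and 0.44 for maxima of 9, 12 and 18.

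**Step 2: how far this depends on the source population.** Rounded bivariate-normal scores clipped to 0–15, after the full rule:

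| Means (SUI, UUI), SD | Source r −0.5 | −0.3 | 0 | +0.3 | +0.5 |
|---|---|---|---|---|---|
| 6, 5, 3.5 | −0.09 | 0.10 | 0.34 | 0.53 | 0.65 |
| 7, 7, 4 | 0.00 | 0.20 | 0.43 | 0.61 | 0.72 |
| 8, 5, 4 | −0.11 | 0.08 | 0.31 | 0.50 | 0.61 |
| 10, 3, 3 | −0.32 | −0.13 | 0.11 | 0.33 | 0.49 |

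In the last row the rule keeps 92% of women at source r = 0, so it rarely binds and shifts the correlation little.

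**Step 3: consequence for separate correlations at n = 50.** Let ρ be the enrolled correlation. Approximate power by Φ(d − 1.96) + Φ(−d − 1.96), with d = atanh|r|·√47 for a simple correlation and √46 for a partial one.

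*Only UUI acts (−0.4).* The SUI correlation is ρ × (−0.4).
- ρ = 0.34: r = −0.136, d = 0.94, nominally significant in 16%.
- ρ = 0.65: r = −0.26, d = 1.82, significant in 45%.
- A joint analysis holds this at 5%.

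*Opposite effects (SUI +0.4, UUI −0.4).* The UUI correlation is −0.4(1 − ρ). The partial correlation has size 0.4√(1 − ρ²)/√(1 − [0.4(1 − ρ)]²).
- ρ = 0.34: simple r = −0.264, d = 1.85, power 46%. Partial r = 0.390 in size, d = 2.79, power 80%.
- ρ = 0.65: simple r = −0.14, d = 0.97, power 16%. Partial r = 0.307 in size, d = 2.15, power 58%.

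Simulation agrees: 15–16% and 45–46% false signals; 47% against 81%, and 16% against 57–58%, for power.

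**Step 4: price of the joint analysis when only one score acts.** The simple correlation of 0.4 gives d = 2.90, power 83%. The partial correlation is 0.4√(1 − ρ²)/√(1 − (0.4ρ)²): 0.380 at ρ = 0.34 (power 77%) and 0.315 at ρ = 0.65 (power 60%). The variance inflation 1/(1 − ρ²) is 1.13 and 1.73, so the scores stay separable.

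**The case against.** The strongest reply is that the plan is underspecified rather than wrong. Symptom scores are not defined, the QUID serves first as an eligibility tool, and the only score the plan builds for severity uses the UDI, UIQ and ISI. The analysis is openly preliminary, no test or alpha is attached to the correlations, and for pure prediction a simple correlation is a legitimate summary. This stands as a limit on how serious the point is. It does not remove it: stress and urge scores are symptom scores on any ordinary reading, and correlation is the only tool named.

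A reader might infer that the rule necessarily makes the two scores positively correlated. The documents do not support that. They give no source correlation or score distribution, and the table shows values at or below zero under a clearly negative source correlation.

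A reader might also infer that separate correlations cannot tell which score matters. That is too strong. When one score alone acts with effect 0.4, it still had the larger absolute correlation in about 95% of simulated trials at enrolled r = 0.34 and 89% at 0.65; across other settings the figure was 82–99%. The cancellation case needs opposite effects, for which the documents give no evidence.

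Nor are the worst figures due to the rule alone. The 45% at enrolled r = 0.65 needs a source correlation of 0.5. Without any selection that would already give an SUI correlation of 0.5 × 0.4 = 0.2, d = 1.39, and about 28% false signals.

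**Conclusion.** The point holds as a modest one. The rule tends to raise the SUI-UUI correlation among enrolled women, and a correlations-only analysis can then credit the wrong score or understate both. With unrelated source scores and the assumptions above, the excess is about 16% against 5% for a false signal, and the loss is about 47% against 80% power if the effects are opposite. These sizes rest on n = 50 inferred from the budget, an assumed 0–15 range, assumed effects of 0.4 and a well-behaved response. They would not carry over to the Improvement Score, a ratio with dry-with-device cases set to 1000. The documents cannot say where in the range this trial will fall; the data will, once the SUI-UUI correlation is reported. This is a cheap improvement to an exploratory analysis, and it leaves the device comparison itself untouched.

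**What to change.** In Data Analysis, list the symptom scores and name the visit QUID SUI and UUI scores among them. Keep the planned correlations. Then add, for example:

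*The correlation between the visit QUID SUI and UUI scores will be reported. The association of response with the two scores will also be examined jointly, by partial Spearman correlation or by regression of the Release Change on both, and each adjusted association will be given with a 95% confidence interval. Poor response will not be attributed to either score on the separate correlations alone.*

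Do not fit a linear slope to the Improvement Score, because the 1000 codes would dominate it. If the Release Change is used, say how women with no leakage without the device are handled, since its denominator is then zero.

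The cost is one extra exploratory analysis on data already being collected. The adjusted intervals are wider when only one score matters (power about 83% falling to 77% at enrolled r = 0.34, and to 60% at 0.65), which is why the separate correlations should stay beside the joint analysis.

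### Every subject wears the intravaginal device, but no step records tolerability, displacement or handling difficulty, so acute tolerability and ease of use cannot be reported

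*Combined protocol and SAP*

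**What the plan says.** All places are in the combined protocol and SAP.

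- **Exposure (Protocol, step 4).** The allocation sentence begins "The subjects will be randomized so that half will perform the Abbreviated Pad Test with the Yoni.Fit device in place followed by repeating without the" (it closes by naming the no-device condition). For the remaining subjects the plan adds: "The other half will perform the challenges in the reverse order". Every subject therefore wears the device once. The challenges listed in step 4 include vigorous coughing and ten jumping jacks.
- **Data taken at the test (step 4).** "The subject then will remove pad, place into bag and seal. The Experimenter will then weigh pad". No question to the subject follows.
- **End of the written steps (steps 5 and 6).** Step 5 calculates scores from the pad weights. Step 6 reads "Patients will be paid \$100 for their participation". No contact after that is described.
- **Endpoints (paragraph before Specific Aims).** The sponsor "proposes to demonstrate short term efficacy with patients suffering from SUI for reduced or eliminated leakage against a standardized battery of challenges as a primary" outcome. Two others, anatomical support and ease of use, are named as secondary.
- **Data Analysis.** Summary statistics, and correlations of the improvement scores with symptom scores and demographics. No summary of events.
- **Background.** On complications of existing devices: "Pessaries have few complications and side effects, however these devices are traditionally placed in the vagina for weeks at a time". On handling and retention, the text says: "Difficulty with self-removal and insertion of the pessary and loss during defecation (Colpexin) may be limiting widespread use of the devices".

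**The concern.** The background presents handling and retention as the weak points of existing devices, and the protocol offers this design as a remedy. The study puts the device into every subject and exercises her with it in place, yet collects nothing on those points. Three things are lost.

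1. **Acute tolerability.** With no recording there is no numerator, so neither a rate nor an upper bound can be given for any event.
2. **Interpretation of the primary measure.** If the device shifts or comes out during the challenges, the with-device pad weight no longer describes a device in place. Nothing in the data would identify that subject.
3. **Ease of use.** It is a named secondary endpoint with no question, scale or observation behind it.

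The results are meant to support applications for research and investor funding. Readers of such applications will ask how subjects tolerated the device, and the study as written would have no answer.

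**Working it through.** **1. What each part of the plan collects**

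| Part of the plan | What it yields | Tolerability, displacement or handling data |
|---|---|---|
| Steps 1–2 | Recruitment, screening questionnaire | None |
| Step 3 | Consent, history, eligibility, four questionnaires (all before the device is worn) | None |
| Step 4 | Two pad weights | None |
| Step 5 | Two scores computed from the weights | None |
| Step 6 | Payment | None |
| Data Analysis | Summary statistics, correlations | None |
| Per-subject costs | Consent, history, questionnaires, height and weight, stipend, referral, coordinator/data management | No item for safety or follow-up |

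**2. Number of women**

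No sample size is stated, so it is inferred from the budget.

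- Per-subject items: 120 + 100 + 100 + 20 + 100 + 125 + 200 = $765, which matches the stated total.
- 38,250 / 765 = 50 women.
- Sensitivity: the $125 item applies to subjects recruited by physician referral. If none incurred it, the cost is 765 − 125 = $640 each, and 38,250 / 640 = 59.8, that is 59 women.

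**3. What recording could show**

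The exact upper bound for 0 events in n is 1 − α^(1/n).

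- n = 50, one-sided 95%: 1 − 0.05^(1/50) = 0.058.
- n = 50, upper limit of a two-sided 95% interval: 1 − 0.025^(1/50) = 0.071.
- n = 59, one-sided 95%: 1 − 0.05^(1/59) = 0.050.
- One test order alone, n = 50/2 = 25, one-sided 95%: 1 − 0.05^(1/25) = 0.113. A table by order is therefore descriptive only.

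The chance of seeing at least one event in 50 women is 1 − (1 − p)^50. The documents give no event rates, so every p here is assumed.

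| Assumed true rate | Chance of at least one event |
|---|---|
| 0.5% | 22% |
| 1% | 39% |
| 2% | 64% |
| 5% | 92% |
| 10% | 99.5% |

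**4. As written**

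Nothing is recorded, so none of these quantities can be computed from the trial's data.

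**The case against.** The best defence is that this is a small feasibility study of acute efficacy with one brief wear in clinic, and that the background describes pessaries as having few complications. The text reviewed is also incomplete: consent pages were removed, the flow chart is not shown and the IRB application is not included, so instructions on reporting harm may sit there. That limits the finding to the visible protocol. It does not supply the missing checklist or table, because the written steps and the analysis section are where they would be carried out.

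The defence also rightly blocks several stronger readings that a reader might infer.

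- **That problems could wait up to seven days for a weekly meeting.** The sentence reads "He will meet with the clinicians as necessary and weekly with [name] to assess progress and solve any problems", and the coordinator's role includes coordinating with the physicians. An as-needed route exists. What is missing is a route and timing specific to reported events.
- **That the background's serious harms are expected with this device.** The pain, infection and bleeding listed there are attributed to surgical mesh. For devices it raises only insertion and removal difficulty and loss during defecation, and the last would not arise in this exercise test.
- **That the device is untested.** The documents cite no earlier human data on it, but do not say that none exist.
- **That subjects who wear the device second go unobserved after removal.** The text does not say when, where or by whom the device is inserted or removed, and weighing, scoring and payment still follow the second test. The asymmetry is a conjecture.
- **That the study is meant to show a safer alternative to surgery.** The stated aim is acute efficacy.

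**Conclusion.** The point stands in its limited form. The visible plan exposes every subject to the device and has no means of reporting acute tolerability, of confirming that the device stayed in place during the with-device test, or of measuring ease of use. This is more than a wording gap, since it decides what data exist at the end. It does not invalidate the planned leakage comparison, so it is a change the sponsor should make, not a fatal flaw.

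As to size, with recording in 50 women the study could exclude event rates above 5.8% (one-sided) if none occurred. It would very probably show an event with a true rate of 5%, and would more often than not miss one at 1%. This rests on the budget-implied 50 women, complete recording in all of them, and assumed event rates. It covers one brief wear and says nothing about longer use. How often displacement would occur, and how far it would alter the pad weights, cannot be estimated from the documents.

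**What to change.** - **Step 4, both test orders.** After the with-device test and device removal, the coordinator completes a short fixed checklist: pain, bleeding, displacement or expulsion during the challenges, difficult insertion or removal, other. The handling items would also supply part of the missing ease-of-use measurement.
- **Later contact (preferable).** One brief call or email to each subject, using the code key the coordinator already holds. The documents give no basis for the interval, so the sponsor should choose and state it.
- **Data Analysis.** Add the number and percentage of women with each event, with exact 95% confidence intervals, overall and by test order.
- **Responsibility.** State who receives and reviews reported events. The sponsor and investigator should set that rule. The two referring physicians have no such role in the present text.

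The cost is one checklist page, one brief contact per subject and one table. No change to the test orders, sample size or primary endpoint is needed. The extra coordinator time is not shown to fit within the $200 coordinator/data management fee, so the budget should be checked. The report may also show a few minor events.

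### Test order is randomised half and half, but the Data Analysis uses it neither in the summaries nor in the predictor correlations

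*Combined protocol and SAP*

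**What the plan says.** Protocol step 4 makes this a two-period within-woman comparison: "The subjects will be randomized so that half will perform the Abbreviated Pad Test with the Yoni.Fit device in place followed by repeating without". For the remaining women it says: "The other half will perform the challenges in the reverse order".

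Step 5 defines two scores per woman. The Improvement Score is net pad weight without the device divided by net pad weight with it. "In case no urine is released with the device in place, the Improvement Score will be defined as" 1000. Release Change is the difference in net weight divided by the net weight without the device.

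Data Analysis is short. "Descriptive statistics will be calculated and include the mean, median, standard deviation". The improvement scores are then correlated with symptom scores and demographics, partly to look for features that predict a poor response. Order is not a stratum, a covariate or a listed variable. The section states no hypothesis test, significance level or sample size.

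On preparation, step 3 says of the women: "They will be instructed to empty their bladders and will be given a liter of water or other drink". Step 4 adds: "An hour after finishing the liter of liquid, the subject is given a tared incontinence pad". Each is described once, before the repeat is mentioned.

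**The concern.** Leakage in a second provocative test on the same visit may differ from leakage in the first, whatever the device does. Randomising the order guards against this on average. Once order is left out of the analysis, however, any first-to-second difference is counted as variation between women. That inflates the reported SD and dilutes the correlations meant to identify women for whom the device works less well.

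The arithmetic mean is also exposed. Both scores are ratios, and balanced order cancels a multiplicative period effect on the log scale but not in the mean of a ratio.

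If order and timing are not kept as data, nobody can tell afterwards whether the two tests differed.

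**Working it through.** The plan gives no power or sample-size figure to reproduce. The steps below use its score definitions, plus assumptions that are marked as such.

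**Inputs**
- From the documents: 1:1 order; the score definitions in step 5; the per-subject budget of $38,250 at $765 each. 38,250 / 765 = 50 women, so 25 per order. This N is inferred, not stated.
- Assumed: second-test leakage = r × first-test leakage. Test-retest log SD is 0.5 for each of the two tests, and the between-woman log SD of response is 0.5, so the log-ratio variance is V = 2(0.5²) + 0.5² = 0.75. The underlying correlation between a predictor and the log ratio is 0.40. The analysis is by rank correlation, two-sided 5%; the plan says only that scores are correlated.

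**1. Effect on one woman's score.** Device first: the without-device test comes second, so the Improvement Score is multiplied by r. Device second: it is multiplied by 1/r. At r = 2 a useless device would score 2.0 in one order and 0.5 in the other.

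**2. Centre.** On the log scale the two orders shift by +ln r and −ln r, and these cancel at 25/25. The median is therefore nearly unbiased. If the evaluable women split 20 device first and 30 device second, a true median ratio of 2 would read about 1.84 at r = 1.5 and 1.69 at r = 2.

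**3. Spread.** With order ignored, the variance of the log ratio is V + (ln r)².
- r = 1.1: 0.750 + 0.009 = 0.759
- r = 1.5: 0.750 + 0.164 = 0.914
- r = 2: 0.750 + 0.480 = 1.230

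A correlation of 0.40 shrinks to 0.40 × √(0.75/0.914) = 0.36 at r = 1.5 and to 0.40 × √(0.75/1.230) = 0.31 at r = 2.

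**4. Mean of the ratio.** Among women who leak in both tests, the mean Improvement Score is multiplied by (r + 1/r)/2: 1.005 at r = 1.1, 1.08 at r = 1.5 and 1.25 at r = 2. Replacing r by 1/r gives the same factor.

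**5. Power to detect a predictor.** Simulation with 25 women per order (at least 20,000 runs per cell, simulation error about 0.3 points). The score is either ranked as it stands or has order partialled out. Women coded 1000 are those with the highest order-free scores and share the top rank. Entries are order ignored v order adjusted, in %.

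| Share coded 1000 | r = 1 | r = 1.5 | r = 2 |
|---|---|---|---|
| 0% | 79 v 78 | 69 v 78 | 54 v 78 |
| 20% | 78 v 77 | 70 v 75 | 61 v 73 |
| 40% | 74 v 73 | 69 v 71 | 65 v 68 |
| 60% | 66 v 65 | 64 v 64 | 62 v 62 |

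At r = 1.1 with none coded, the result is 78–79% v 78%, so there is no gain. The r = 1 column shows the price of adjusting when there is no period effect: about one point.

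**The case against.** **The size depends on unknowns.** Nothing in the documents supports r = 1.5 or r = 2, and the 54% v 78% contrast is the most favourable cell. The background section expects the device to eliminate or greatly reduce leakage. If many women are dry with it, the 1000 code takes over the ranking and the gain largely disappears. If raw scores with 20% coded 1000 were correlated by Pearson's method, nothing would be gained at any r. All of this stands and limits the point.

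**The study is descriptive.** Power is quoted for a test the plan does not specify, as a measure of lost information. The effect on means is also not the largest problem with them. Under the same assumptions, test-retest noise alone multiplies the mean ratio by exp(0.25) = 1.28, against 1.25 for r = 2. One coded woman in 50 moves a mean of 2.57 to (49 × 2.57 + 1000)/50 = 22.5. Order adjustment removes neither effect.

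**Two stronger readings are tempting but not supported.**
- A reader might infer that ignoring order makes the device look falsely effective. With balanced orders it does not: the median is nearly unbiased, and a pooled test, had one been planned, would become conservative.
- A reader might infer that bladder load is left uncontrolled in the repeat test, against the aim of testing "in a standardized set of challenges performed with and without Yoni-Fit in place". The text is ambiguous rather than clearly deficient. The one-hour wait sits within step 4's account of the pad test, so repeating that test may include it, although the void and the litre are in step 3. The protocol also says "The flow chart for the study is shown in the figure below"; that figure is not available here, nor is the pad-test publication that step 4 cites. Either may settle it.

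**Conclusion.** The point holds: order is randomised and then left out of the planned analysis. What is mainly lost is efficiency in the predictor search, not validity of the central estimate. The loss is about 9 points of power at r = 1.5 and 24 at r = 2 with no coded scores. At r = 2 it falls to about 12 points with 20% coded, 3 with 40% and none with 60%. It is nil at r = 1.1 whatever the coding.

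These figures rest on an inferred N of 50, an assumed correlation of 0.40, an assumed log-ratio variance of 0.75, a rank analysis and an unknown r. Importance is minor to moderate. The change is worth making because it costs almost nothing and because order and timing have to be captured prospectively. The bladder preparation for the repeat test is a request for clarification only.

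**What to change.** 1. Record each woman's test order and the start time of both tests.
2. Report the median Improvement Score and the median Release Change by order and overall. Keep women who are dry only with the device in Release Change, at their defined value of 100%.
3. Include order as a covariate in the predictor correlations, on ranks, with the 1000 code as the extreme rank.
4. As a clarification, say in step 4 whether the timed bladder preparation in steps 3 and 4 also applies to the repeat test, or point to the flow chart or the cited pad test if either says so.

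Cost: the order code and two time fields on the record form, a few words in Data Analysis and one sentence in step 4. Statistically it takes one degree of freedom, about one point of power if there is no period effect. No procedure or hypothesis test is added.
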